#### 2.4.2 Prior, concomitant and post therapies

The FAS will be used for the analyses below.

The number of subjects using rescue treatments as defined in section 6.2.3 of the CSP will be summarized by treatment group for the periods pre-randomization, during on-treatment period and after on-treatment period. Listings will display the kind and duration of all ITP-directed pre-treatments and rescue medications separately.

For analyses of rescue medication (e. g. dose, time point, etc.) the Data Review committee decided which doses of dexamethasone, eltrombogag and other ITP-directed therapies were used as rescue medication and as study treatment. Concomitant medications (of any type, i.e. classified as rescue medication or not) and significant non-drug therapies prior to and after the start of the study treatment will be listed and summarized according to the Anatomical Therapeutic Chemical (ATC) classification system, by treatment group.

### 2.5 Analysis of the primary objective

#### 2.5.1 Primary endpoint

The primary objective is to compare the ability of both study treatments to induce sustained response off treatment at 52 Weeks.

The primary endpoint is the proportion of patients with sustained response off treatment at 52 weeks (i.e. until study visit Week 53).

Sustained response off treatment is defined as:

- reach platelet count  $\ge 30 \times 10^9$ /L and then maintain platelet counts  $\ge 30 \times 10^9$ /L after discontinuation of study treatment AND
- maintain platelet count  $\ge 30 \times 10^{9}$ /L in the absence of bleeding events  $\ge$  Grade II AND
- without the use of any rescue therapy (see Section 6.2.3 of CSP) until week 52

Details on Response or non-response are assessed during the Data Review Meeting and documented accordingly.

For the primary and supportive analyses the FAS will be used.

### 2.5.2 Statistical hypothesis, model, and method of analysis

The analysis of the primary endpoint will be based on the following estimand:

The population will be the FAS;

Variable of interest: The primary endpoint is the response rate in terms of sustained response off treatment at 52 weeks (i.e. until study Visit Week 53), in absence of bleeding or use of rescue therapy as defined above, i.e. a composite estimand.

Intervention effect: effect of eltrombopag in combination with a short course of high-dose dexamethasone versus 1-3 cycles of high-dose dexamethasone alone at 52 weeks, regardless of adherence to randomized treatment.

Summary measure: odds ratio

The statistical hypothesis to be rejected is that the rates of patients achieving sustained response at 52 weeks are equal in both treatment groups. The corresponding alternative hypothesis is that the rates are not equal under eltrombopag combined with a short course of high-dose dexamethasone, compared to 1-3 cycles of high-dose dexamethasone monotherapy.

Let  $p_A$  and  $p_B$  denote the proportions of patients achieving sustained response off treatment for the treatment groups:

A = eltrombopag combined with a short course of high-dose dexamethasone

B = 1-3 cycles of high-dose dexamethasone "standard"

The following hypotheses will be tested:

H0:  $(p_B / (1 - p_B)) / (p_A / (1 - p_A)) = OR_{B/A} = 1$ 

versus HA:  $(p_B / (1 - p_B)) / (p_A / (1 - p_A)) = OR_{B/A} \neq 1$ 

In other words:

H0: The rate of patients achieving a sustained response off treatment at 52 weeks in the eltrombopag plus a short course of high-dose dexamethasone arm is equal to the respective rate in the 1-3 cycles high-dose dexamethasone monotherapy "standard" arm (corresponding to equal odds).

HA: The rate of patients achieving a sustained response off treatment at 52 weeks in the eltrombopag plus a short course of high-dose dexamethasone arm is higher than the respective rate in the 1-3 cycles of dexamethasone monotherapy "standard" arm.

The primary analysis will be performed comparing the treatment groups with respect to the primary efficacy outcome, based on the Odds Ratio, in a Logistic Regression model with the factor treatment and cofactors ITP-directed pre-therapy ("no" vs. "yes" during 3 days before randomization), screening platelet count (quantitative) and age ( $\leq$  vs. >60 yrs). The odds ratio and its 95% confidence interval (CI) and p-value will be given. The null hypothesis of equal odds will be rejected if the 2-sided p-value from the logistic regression model for the factor "treatment" is <0.05; however, superiority of eltrombopag in combination with a short course of dexamethasone will be claimed only if the direction is correct, i.e. if the odds of response are higher under eltrombopag plus a short course of high-dose dexamethasone compared to 1-3 cycles of dexamethasone monotherapy (ORB/A < 1)

In case the analysis result is revealed to be unstable / does not converge due to cells with too low numbers, the covariates age and ITP-directed pre-therapy may be removed, until valid results are seen. This will be checked during dry run preparation, i.e. before the data have been unblinded, to warrant avoidance of data-driven decision making. Furthermore, during this process, an analysis using an exact logistic regression model (StatXact) may be considered.

<sup>3 For pretreated patients the last platelet count before pre-treatment was started

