12.4.2 Statistical model, hypothesis, and method of analysis

The analysis of the primary endpoint will be based on the following estimand:

The population will be the Full Analysis Set;

Variable of interest: The primary endpoint is the response rate in terms of sustained response off treatment at 52 weeks, in absence of bleeding or use of rescue therapy as defined above, i.e. a composite estimand.

Intervention effect: effect of eltrombopag in combination with a short course of high-dose dexamethasone versus 1-3 cycles of high-dose dexamethasone alone at 52 weeks, regardless of adherence to randomized treatment.

Summary measure: odds ratio

The statistical hypothesis to be rejected is that the rates of patients achieving sustained response at 52 weeks are equal in both treatment groups. The corresponding alternative hypothesis is that the rates are not equal under eltrombopag combined with a short course of high-dose dexamethasone, compared to 1-3 cycles of high-dose dexamethasone monotherapy.

Let p_A and p_B denote the proportions of patients achieving sustained response off treatment for the treatment groups:

A = eltrombopag combined with a short course of high-dose dexamethasone

B = 1-3 cycles of high-dose dexamethasone "standard"

The following hypotheses will be tested:

H₀: $(p_B / (1 - p_B)) / (p_A / (1 - p_A)) = OR_{B/A} = 1$

versus H_A : $(p_B / (1 - p_B)) / (p_A / (1 - p_A)) = OR_{B/A} \neq 1$

In other words:

 H_0 : The rate of patients achieving a sustained response off treatment at 52 weeks in the eltrombopag plus a short course of high-dose dexamethasone arm is equal to the respective rate in the 1-3 cycles high-dose dexamethasone monotherapy "standard" arm (corresponding to equal odds).

 H_A : The rate of patients achieving a sustained response off treatment at 52 weeks in the eltrombopag plus a short course of high-dose dexamethasone arm is higher than the respective rate in the 1-3 cycles of dexamethasone monotherapy "standard" arm.

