12.8 Sample size calculation

12.8.1 Primary endpoint

This trial is intended to estimate the difference in the rates of patients achieving a sustained response off treatment at Week 52.

(sustained response off treatment = maintain platelet $\geq 30 \times 10^9/L$ after treatment discontinuation in the absence of bleeding events \geq Grade II or use of any rescue medication at all visits until Week 52)

The sample size calculation is based on the following assumptions:

- 1. Sustained response off treatment is achieved in 30% of the patients in the dexamethasone arm and 65% in the eltrombopag + dexamethasone arm
- 2. Randomization is allocated in a 1:1 ratio (eltrombopag + dexamethasone: dexamethasone)
- 4. A two-sided 5% level of significance will be applied.
- 5. The study will have 90% power under the stated assumptions for the primary endpoint.

Based on these assumptions, a total of 47 patients in each treatment arm would need to be randomized. More conservative scenarios based on lower treatment effects and 50 patients per group, assuming rates of 30 versus 60% would lead to a power of 81%, and 30 versus 55% would still allow for a power of 64%, whereas the radius of the respective confidence interval would be between 0.20 and 0.21 based these scenarios.

To allow for some dropouts / protocol violations, a total of 106 patients is planned to be enrolled.

Due to feasibility reasons, resulting in a substantial delay in recruitment, as described above, with Amendment 3 recruitment will be prematurely discontinued. A final number of ca. 24 patients is expected to be recruited by the time of approval.

The patients enrolled by then will be analyzed and reported as described, to allow for adequate use of the present data.

Based on the assumptions described, the resulting power will be ca. 24%. As a consequence, all analyses will be performed in a purely descriptive manner.

13 Ethical considerations and administrative procedures

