- Number of patients who are able to discontinue eltrombopag and dexamethasone with  $PLT \ge 30 \times 10^{9}/L$

- Number of patients with loss of response after treatment discontinuation
- Number of patients with bleeding events after treatment discontinuation
- Number of patients receiving rescue treatment

The descriptive primary analysis but not the logistic regression will be repeated in the subgroups mentioned in section 2.2.1 Subgroup of interest.

If a covariate lead to (quasi) complete separation of the model, the model will be modified. Then, this covariate will be skipped from the model.

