# 3 Sample size calculation

This trial is intended to estimate the difference in the rates of patients achieving a sustained response off treatment at Week 52.

The sample size calculation is based on the following assumptions:

- 1. Sustained response off treatment is achieved in 30% of the patients in the dexamethasone arm and 65% in the eltrombopag + dexamethasone arm
- 2. Randomization is allocated in a 1:1 ratio (eltrombopag + dexamethasone: dexamethasone)
- 4. A two-sided 5% level of significance will be applied.
- 5. The study will have 90% power under the stated assumptions for the primary endpoint.

Based on these assumptions, a total of 47 patients in each treatment arm would need to be randomized. More conservative scenarios based on lower treatment effects and 50 patients per group, assuming rates of 30 versus 60% would lead to a power of 81%, and 30 versus 55% would still allow for a power of 64%, whereas the radius of the respective confidence interval would be between 0.20 and 0.21 based these scenarios.

To allow for some dropouts/protocol violations, a total of 106 patients is planned to be enrolled.

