#### 5.5 Statistical models

#### 5.5.1 Primary analysis

Proc logistic is used. The SAS code will be implemented in the TFL shells as programming note.

Rescue medication will be identified by the respective yes/no-items in the forms "Prior/Concomitant medication", "Procedures and Non-drug therapy", "WHO Bleeding Scale", "Dosage administration record for Eltrombopag", and "Dosage administration record for Dexamethasone". During the data review meeting the medication of each patient was reviewed and considered if the investigators' classification as rescue medication (yes or no) is reasonable. Unambiguous cases were overruled. For example when only the first episode but not the subsequent episodes were classified as a rescue medication by the investigator.

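### At about 24 patients the four-term logistic model overstates the odds ratio on average if the design effect is true, and no estimate or interval is planned for the rate difference the trial says it will estimate

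*SAP*

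**What the plan says.** SAP 2.5.2 compares the arms "in a Logistic Regression model with the factor treatment and cofactors ITP-directed pre-therapy", screening platelet count (quantitative) and age (up to 60 versus over 60). It reports the odds ratio with a 95% CI and p-value. SAP 5.5.1 adds "Proc logistic is used" and names no penalised option. SAP 2.7.1 applies the same analysis to the three binary secondary endpoints: overall response at Week 52, overall response by Week 4 and complete response by Week 4.

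There are three fallbacks:

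- SAP 2.5.2 allows age and pre-therapy to be taken out if the fit is unstable or fails to converge.
- SAP 2.5.2 also allows exact logistic regression to be considered.
- SAP 2.5.4 says "If a covariate lead to (quasi) complete separation of the model, the model will be modified", and the covariate responsible is then left out.

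On the quantity of interest, Protocol 12.8.1 says "This trial is intended to estimate the difference in the rates of patients achieving a sustained response off treatment at Week 52", and SAP 3 repeats it. The estimand in Protocol 12.4.2 says "Summary measure: odds ratio", as does SAP 2.5.2. For proportions, the general methods in both documents provide frequencies, percentages and Clopper-Pearson intervals for selected parameters that are not named.

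After Amendment 3, Protocol 12.8.1 expects about 24 patients and about 24% power, with descriptive analysis only. SAP 3 does not carry these figures.

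**The concern.** In a descriptive trial the effect estimate and its interval are the result. Maximum-likelihood logistic regression is biased away from an odds ratio of 1 when there are few events per parameter, even when it converges without any warning. Here four slopes rest on about 11 responders and 13 non-responders. SAP version 3.0 was updated for Amendments 1 to 3, but the estimation method was not revisited.

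The second gap needs no simulation. The sample-size sections promise an estimate of a difference and quote the width of its interval, but no analysis section produces either. A reader could subtract two percentages and would have no planned measure of uncertainty for the result.

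**Working it through.** **Inputs from the documents.** "Sustained response off treatment is achieved in 30% of the patients in the dexamethasone arm and 65% in the eltrombopag + dexamethasone arm"; "A two-sided 5% level of significance will be applied"; "The study will have 90% power under the stated assumptions for the primary endpoint" (SAP 3). Also 1:1 allocation, 47 per arm, and a CI radius of 0.20 to 0.21 at 50 per group; after Amendment 3, about 24 patients (taken as 12 per arm) and about 24% power.

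**Step 1: reproduce the plan's figures.** The power formula is the pooled two-proportion normal formula with a 1/n continuity correction:

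power = Φ{[d − 1/n − 1.96√(2p̄(1−p̄)/n)] / √([pA(1−pA)+pB(1−pB)]/n)}

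- At n = 12, d = 0.35 and p̄ = 0.475: (0.35 − 0.0833 − 0.3996)/0.1909 = −0.696, so power is 24.3% (plan: 24%).
- At n = 47, power is 90.6% (plan: 90%).
- At n = 50, power is 81.5% for 30% vs 60% and 64.8% for 30% vs 55% (plan: 81% and 64%).
- The radius is 1.96√([pA(1−pA)+pB(1−pB)]/n) + 1/n. At n = 50 it is 0.206 (30% vs 60%) and 0.207 (30% vs 55%), which matches 0.20 to 0.21. The quoted radius is therefore that of a rate difference.

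**Step 2: information at 12 per arm.** Expected responders are 12 × 0.30 + 12 × 0.65 = 11.4, and non-responders 24 − 11.4 = 12.6. The true odds ratio is (0.65/0.35)/(0.30/0.70) = 4.33.

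**Step 3: behaviour of the model.** This was simulated with 6,000 to 20,000 trials per scenario. The documents give no covariate distributions, so these are assumptions: prevalences of the two binary covariates from 0.15 to 0.7, platelets uniform from 0 to 30, and covariate effects from none to ±1 log-odds. Maximum-likelihood (ML) figures exclude fits that failed.

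| Model (true OR 4.33) | Geometric-mean OR | Median OR |
|---|---|---|
| ML, full model, 12 per arm | 6.1–6.5 (+41% to +50%) | 5.6–5.9 (+30% to +36%) |
| ML, age and pre-therapy dropped only if the full model fails | +43% to +53% | +30% to +38% |
| ML, treatment and platelets only | 5.36 (+24%) | 4.90 (+13%) |
| ML, treatment only | 4.84 (+12%) | 4.20 (−3%) |
| Firth, full model, 12 per arm | 4.4–4.7 | 3.9–4.2 |
| ML, full model, 47–53 per arm | 4.7–4.8 (+8% to +11%) | 4.7 (+8%) |

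The full model failed to converge or separated in 7 to 14% of trials, and in 37% when pre-therapy prevalence was 15%. A separate run of 4,000 trials per scenario (pre-therapy 50%, age over 60 40%, platelets uniform 1 to 29, with and without covariate effects) gave geometric means of 6.3 to 6.9 and a median of 5.9. The upper end therefore depends on the covariate assumptions.

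**Step 4: other effect sizes, full ML model.**

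- 30% vs 60% (OR 3.50): geometric mean +41%, median +30%.
- 30% vs 55% (OR 2.85): geometric mean +35%, median +24%.
- No effect: geometric mean +1%, median 0%.

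**Step 5: precision of the difference at 12 per arm.**

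- Uncorrected Wald: 1.96√((0.21 + 0.2275)/12) = 0.374.
- The documents' own formula: 0.374 + 1/12 = 0.46.
- Newcombe, mean half-width over all possible outcomes: 0.32.

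As an illustration, 8/12 versus 4/12 gives a difference of 0.33 (Newcombe 95% CI −0.06 to 0.61) and an unadjusted odds ratio of 4.0 (0.73 to 21.8).

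**The case against.** The SAP is not without small-sample provisions. Its trigger includes instability as well as non-convergence, exact logistic regression is a recognised small-sample method, and dropping covariates does reduce the bias (median +13% with treatment and platelets). This stands as credit to the plan. But removal and the exact method are optional, and a fit that converges normally would not trigger any of them. Applying the removal rule only when the full model fails left the bias essentially unchanged.

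The average inflation is also small beside the uncertainty. Wald intervals from the ML fits covered the true value in 97 to 98% of simulated trials, and the upper limit was typically about 70 times the lower. That lessens the danger of a misleading conclusion, but it does not correct the point estimate.

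Three stronger readings are tempting, and the documents do not support them:

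- A reader might infer that the reported odds ratio will be inflated whenever the model fits. Bias is an average: about 40% of converged fits fell below the true odds ratio.
- A reader might take a single figure such as 45% as a property of the plan. It depends on the design effect being true, on the scale of averaging and on assumed covariates.
- A reader might call the 0.20 to 0.21 radius an error. Protocol 12.8.1 ties it to 50 per group and then gives the new number and power. Restating it is an addition, not a correction.

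The odds ratio is, finally, the declared summary measure, and the crude difference follows from the per-arm percentages. What is missing is a planned estimate of that difference with an interval.

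**Conclusion.** The point holds in a conditional form. If the design effect is true, the full model at 12 per arm overstates the odds ratio by roughly 30% on the median and up to about 50% on the geometric mean, among converged fits and under assumed covariate distributions. The bias is smaller for smaller effects and about nil under no effect. It comes from the reduced sample: at 47 to 53 per arm the same model is off by only 8 to 11%. The fallbacks do not correct most converged fits.

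That no estimate or confidence interval is planned for the rate difference follows from the text alone and rests on no assumption. The change is worth making but is not critical, because the analysis is already declared descriptive and the interval around the odds ratio will be very wide.

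**What to change.** - **SAP 2.5.2 and 5.5.1:** report the per-arm responder rates and their difference with a Newcombe or Miettinen-Nurminen 95% CI. Fit the prespecified logistic model with Firth's penalised likelihood and a profile penalised-likelihood CI, which is an option within PROC LOGISTIC. This also handles separation, so covariates need not be dropped.
- **SAP 2.7.1:** apply the same to the three binary secondary endpoints.
- **Protocol 12.8.1 and SAP 3:** next to the 24% power, state the expected half-width for the difference at 12 per arm: about 0.46 by the documents' continuity-corrected formula, about 0.37 for uncorrected Wald and about 0.32 for Newcombe.

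The cost is one model option and one extra table column, with no new data. The odds ratio will on average look less dramatic, and Firth's median sits slightly below the true value (3.9 to 4.2 against 4.33). An unadjusted exact odds ratio would be a defensible alternative to Firth, provided it is fixed in advance. In the simulations the rate difference averaged 0.34 against a true 0.35, over trials in which a model could be fitted.

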6.4 Treatment blinding

Treatment will be open label to subjects, investigator staff, persons performing the assessments, and the clinical trial team.

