# Document History – Changes compared to previous final version of SAP

Date	Time point	Reason for update	Outcome for update	Section and title impacted (Current)
23- OCT- 2019	Prior to FPFV	Creation of 1st draft version by CRO- Statistician	For review of Novartis MA / TS	NA
09- JAN- 2020	Prior to FPFV	Review by Sponsor	Second draft for finalization	NA
13- MRZ- 2020	Prior to FPFV	Finalization Version 1.0	NA	NA
18- JUN- 2020	Prior to FPFV	Version 2.0 after review of TFLs	Algorithm for "Eligibility of discontinuation of study medication" was added	5.5.1.2
			Duration of sustained response: "from start of study treatment until loss of response " correted analogously to CSP- Update	2.7.1
			Dry run (before unblinding the study team) to check the convergence of the primary logistic model including several covariates included	2.5.2
16- NOV- 2023	Prior to DBL	Version 3.0 due to CSP amendment No. 2 and 3; 1st and 2nd DRM	Adaption to CSP amendment no. 2 and no. 3. As well as decisions from the first and second Data Review Meeting regarding analysis. Agreement on SAP, version 3.0, prior to DBL, signature shortly after DBL	

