#### 5.5.1.1 Algorithm to derive the parameter "sustained response off treatment"

The parameter was assessed by the Data Review Committee, see data Review Meeting Minutes.

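### The SAP says covariate removal from the primary model is protected by blinding, but the trial is open label and neither document describes any masking of the analysis

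*SAP*

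**What the plan says.** **The primary model.** Protocol 12.4.2 and SAP 2.5.2 specify a logistic regression of sustained response on treatment, ITP-directed pre-therapy, screening platelet count and age group.

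**The removal rule.** For a fit that is unstable or does not converge because of sparse cells, SAP 2.5.2 adds that "the covariates age and ITP-directed pre-therapy may be removed, until valid results are seen". It also says that "an analysis using an exact logistic regression model (StatXact) may be considered". The stated protection is that the check belongs to the dry run, "before the data have been unblinded, to warrant avoidance of data-driven decision making". The SAP document history names the party taken to be blinded: "Dry run (before unblinding the study team) to check the convergence of the primary logistic model including several covariates included".

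**The blinding.** Protocol 6.4 reads: "Treatment will be open label to subjects, investigator staff, persons performing the assessments, and the clinical trial team".

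**A second rule.** SAP 2.5.4 states: "If a covariate lead to (quasi) complete separation of the model, the model will be modified". It continues: "Then, this covariate will be skipped from the model". No time point is attached.

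**The outcome variable.** SAP 5.5.1.1 gives no algorithm for sustained response: "The parameter was assessed by the Data Review Committee, see data Review Meeting Minutes".

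**Status of the results.** The data analysis entry of the protocol summary and Protocol 12.8.1 make all analyses purely descriptive after Amendment 3, with about 24 patients and about 24% power.

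**The concern.** Changing the covariate set changes the treatment odds ratio, its confidence interval and its p-value. Doing so after looking at the data is acceptable if the rule is mechanical, or if whoever decides cannot see the results by arm. The SAP relies on the second condition, and the documents do not establish it. The rule is not mechanical either: it sets no threshold for instability, no order for dropping the two covariates, and no trigger for the exact model. A reader of the study report could not tell whether the model presented was the only one the plan allowed, or one of several chosen with the arms visible.

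**Working it through.** **1. The plan's own figures.** Inputs from Protocol 12.8.1 and SAP 3: 30% versus 65%, 1:1 allocation, two-sided 5%, 90% power.

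- Uncorrected: n = [1.96·√(2·0.475·0.525) + 1.2816·√(0.30·0.70 + 0.65·0.35)]² / 0.35² = (1.384 + 0.848)² / 0.1225 = 40.7, so 41 per arm.
- With continuity correction: (40.7/4)·[1 + √(1 + 4/(40.7·0.35))]² = 46.2, so 47 per arm, as stated.
- Power at 12 per arm with the correction: Φ[(0.35 − 1/12 − 1.96·√(0.49875/12)) / √(0.4375/12)] = Φ(−0.133/0.191) = Φ(−0.70) = 24%, as stated.

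The sample-size figures are not in question. They fix the setting for what follows.

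**2. How sparse the data are.** Expected responders are 12·0.30 + 12·0.65 = 11.4 of 24. Four coefficients besides the intercept leave 11.4/4 = 2.9 responders per coefficient. At 30% in both arms it is 7.2/4 = 1.8.

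**3. What the rules permit.** SAP 2.5.2 allows four covariate sets (both covariates, age only, pre-therapy only, neither), with treatment and screening platelet count always kept, plus an exact model. SAP 2.5.4 applies to any covariate, so it could also remove screening platelet count.

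**4. Whether anyone is masked.** The document history speaks of unblinding the study team; Protocol 6.4 says the clinical trial team knows the treatment. SAP 5.1 has the data review meeting settle the date treatment stopped by inspecting dosing records, under rules that differ by randomised arm. SAP 2.5.1, 5.5.1 and 5.5.1.1 have response and rescue use settled in the same patient-level review. No masked analyst, dummy code, restricted by-arm output or unblinding event is described.

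**5. How often the trigger would be met.** Simulation with 12 per arm. These inputs are assumptions, because the documents give no covariate frequencies: age over 60 in 30% to 50%, pre-therapy in 15% to 50%, screening platelet count uniform on 1 to 29, covariate log-odds effects of 0 or 0.7.

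- 30% versus 65%, age over 60 in 40%, pre-therapy in 50%: the full model fails in about 9%.
- 30% in both arms: from about 10% (both covariates at 50%) to 47% (age over 60 in 30%, pre-therapy in 15%).
- At the planned 106 patients (30% in both arms, both covariates at 50%): no failures in 1,500 runs.

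**6. What the stated trigger could do at worst.** Use the full model when it fits. When it fails, take the reduced model with the smallest Wald p-value. Under the full model alone, a failed fit counts as not significant. Covariates have no effect.

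| Scenario | Full model only, p<0.05 | With adverse use of the trigger |
|---|---|---|
| 30% vs 65%, age over 60 in 40%, pre-therapy 50% | 26% | 31% |
| 30% vs 65%, rarer covariates | 22% | 36% |
| 30% in both arms | 2.4% | 2.9% |
| 47.5% in both arms | 3.8% | 4.3% |

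A repeat run gave 29% to 34% and 22% to 37% for the first two rows, and stayed below 5% under no effect. The level shifts by a few points between runs; the rise of about 5 points in the first row does not. Part of every rise is simply a trial gaining an estimate where it had none.

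**7. The estimate itself.** At 30% in both arms, across the permitted models that could be fitted, the largest odds ratio divided by the smallest had a median of 1.2 to 1.3 and a 90th percentile of 1.8 to 2.8. Many of these trials did not meet the trigger, so this shows how sensitive the estimate is to the model, not what the rule would produce.

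**The case against.** **Removal is conditional.** It is allowed only for an unstable or non-converging fit, and in that sentence valid most naturally means estimable, not favourable. SAP 2.5.2 names two covariates only. The SAP 2.5.4 rule is mandatory, tied to the covariate causing separation, and placed among supportive analyses. This stands, with two limits: instability is undefined, and it is unclear whether SAP 2.5.4 also governs the primary model.

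**The rule predates the data.** The dry run entered with SAP version 2.0, before the first patient. That is to the sponsor's credit, but the decision under the rule comes later. Version 3.0 was agreed before database lock and signed shortly after.

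**An open-label trial can have a masked analyst.** A CRO does the analysis, and a dry run on dummy codes is feasible. It would even be informative: in the simulations, the model without treatment also failed in 21% to 96% of full-model failures, so separation can often be seen without the arm. This stands against any claim that masking is impossible. It does not supply masking that the documents leave out, and dummy codes cannot fully test a model whose convergence also depends on the true arm-by-response cells.

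**A larger effect is tempting to quote.** Taking the best of four models in every trial gives p<0.05 in about 42%, against 30% for the full model. That assumes free choice even when the full model fits, which SAP 2.5.2 does not grant.

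**The analyses are descriptive.** This lowers the stakes. It does not remove them: the odds ratio and its interval are the descriptive result, SAP 2.5.2 still carries a p<0.05 superiority rule, and SAP 2.7.1 reuses the analysis for overall response and for the Week 4 response endpoints.

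**Conclusion.** The point holds in a limited form. The SAP justifies discretionary covariate removal by a blind that, as documented, does not cover the study team it names. No other masking is described, and the trigger and removal order are left open.

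A reader might infer that the model was, or will be, chosen for its result. The documents do not show that; they fail to rule it out while claiming to.

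At about 24 patients the rule has a material chance of being used: roughly 9% to 47% of simulated trials, depending on covariate frequencies that are assumed. Under the stated trigger, adverse use adds about 5 percentage points to the chance of p<0.05 at 30% versus 65%, and about 14 with rarer covariates (36 − 22). Wald type I error stays below 5% in these scenarios, so false positives are not the main issue. The main harm is an odds ratio and interval whose model cannot be shown to have been fixed in advance. Descriptive reporting bounds the consequence.

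**What to change.** In SAP 2.5.2, fix one model (treatment, screening platelet count, age group, pre-therapy) and one method that stays finite under separation, for example Firth penalised likelihood with a profile-likelihood confidence interval. Exact logistic regression is an acceptable alternative if it is named as the single fallback with an objective trigger, such as separation reported by the fitting procedure. Delete the covariate-removal rules in SAP 2.5.2 and 2.5.4, and delete the statement that the decision precedes unblinding.

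If SAP 3.0 is already final, record this as a documented change in SAP 4, which currently reports none, and present the originally specified model beside the new one, stating whether it converged.

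The cost is SAP wording, one option in the logistic procedure, and slight shrinkage of the estimate with the penalised method. No new data are needed.
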